# 7.6 Exercise Testing and Training

## 7.6.1 VO2max Test and Blood Lactate Levels

Subjects will perform an incremental cycling test to volitional fatigue on an electronically braked cycle ergometer (such as Monark E839, Varberg, Sweden). To measure oxygen uptake and determine VO2max an online gas collection system (e.g. COSMED CPET) will be used where O2 and CO2 concentration in the expired gas are continuously measured and monitored as breath-by-breath values.

Subjects will be asked to refrain from heavy exercise 24h prior to the test, and consuming caffeine or alcohol 12h prior to the test. Measurements will begin with the subjects resting for 3 min seated on the bike ergometer whereafter the workload will be increased by 25W every 60 sec until volitional fatigue. Subjects should keep cadence between 60 and 90 rpm during the test. Mean VO2max will be determined as the highest O2 value averaged over 30 s for each subject. At VO2max the following parameters will be recorded: ventilation (l/min) respiratory rate, VCO2 (l/min), respiratory exchange ratio (RER, [VCO2 / VO2]).

In addition at V4, the maximal heart rate and the maximal work rate will be recorded in order to design the training program.

At V3 and V43, capillary (fingertip or earlobe) blood samples will be obtained at rest and at each 25W workload increased and analysed for lactate (e.g. Radiometer ABL80 or similar). Blood collection should be started 40-45 seconds into the workload and no blood sample should be obtained at maximal effort. The final blood sample should be obtained within 5 minutes after termination of the bike exercise. Heart rate and oxygen uptake (VO2) will be recorded at rest at each 25W increase.

After the test subjects will rest for  $60\pm5$  min and will be offered water *ad libitum* and a light snack e.g. fruit, chocolate or bar. The snack has to be consumed at least 30 min before the upcoming exercise capacity test (not applicable for V1).

Data and information contained in this document are considered to constitute trade secrets and confidential commercial information, and the legal protections provided to such trade secrets and confidential information are hereby claimed under the provisions of applicable law. No part of this document may be publicly disclosed without the written consent of Philip Morris Products S.A

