# **Confidentiality Statement**

_
F
RENT
Щ.
r
R R
5
5
0
~
-01-EU,
ш
1
Ξ
Y
ġ
Ň
ш
Ϋ.
P1-EXC-0
1
CSP CSP
ഗ
C
ന്
133
2
140
8
02
62
MFO
$\leq$
ົດ
ଚ୍ଚ
~'
of RD
Ľ
Ť
0
copy
o
cob
ed
e
2
Ę
ō
õ
uncontrolle
an
0
Ħ
P
ž
Ĕ
nuc
ocum

This

Philip Morris Products SA Clinical Study Protocol

P1-EXC-01-EU

Version 3.0 / 2 May 2019

Confidential

5
1
Ŧ
0
4
à
—
O
_pt
g
Р

	Screening	Familiarization	Baseline	Exercise Tests Acute Effect	Training Visits	Medical Visit	Training Visits	Medical Visit	Training Visits	Exercise Tests Training Effect	Discharge / Early Termination	28-day Safety follow-up
Visit	~	2	ę	4	5-14	14	15-28	28	29-42	43	44	
rebreathing, and COHb after CO-rebreathing.												
Perceived exertion - RPE Borg scale 			•							٠		
Blood COHb%			•	•		•		•		٠		
Capillary blood lactate levels 			•							٠		
Blood sampling for biological health markers 						•		•		٠		
Spot urine collection for urinary exposure markers (NEQ, NNAL, CEMA, creatinine) 			•	•		•		•		•		
Biobanking sample collection-blood, urine, saliva			•			•		•		٠		
Biobanking sample collection- sweat			•							٠		

 Rate of perceived exertion will be measured at rest and at every 25 W increase during the VO2 max test until the end of the test.

 Capillary (fingertip or earlobe) blood samples will be obtained at rest and at each workload and analysed for lactate. Blood collection should be started 40-45 sec into the workload and no blood sample should be obtained at maximal effort. The final blood sample should be obtained 60 sec after termination of the bike exercise.

 Blood sampling will be performed on fasting state (at least 8 hours of fasting).

 Urine collection to be performed as late as possible during the day.

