The SAS procedure PROC MIXED will be used to estimate the differences in blood composition parameters (V43) and respiratory parameters (V4 and V43) from baseline (V3) with age, sex, Ccigarette consumption at V1 and daily cigarette consumption as covariates. For the respiratory parameters, visit and visit*arm will be covariates in addition to those specified previously. Also the baseline values of the parameters (V3) will be considered as a covariate and other clinically relevant covariates of interest may be added as deemed appropriate. The dependent variable will be the change from baseline.

Endpoints to be analyzed as physiological parameters (V43) are the following blood composition parameters

- Hemoglobin mass (g)
- Red blood cell volume (mL)
- Plasma volume (mL)
- Total blood volume (mL)

Endpoints to be analyzed as respiratory parameters (V4 and V43) are the following

- Ventilation (L/min)
- Respiratory rate
- VCO2 (L/min)
- Respiratory exchange ratio (RER) (VCO2 / VO₂).

Estimates of the endpoints and their 95% confidence intervals within each arm will be reported and also differences between arms (see Table 4 for analysis related to V4 and Table 5 for V43) will be estimated and reported together with their 95% confidence intervals. Boxplots of each

Confidentiality Statement

Philip Morris Products SA.	Statistical Analysis Plan	Confidential
P1-EXC-01-EU	Final 2.0	Page 44 of 71
Related to PMI-RRP-WKI-112487		SAP P1-EXC-01-EU

physiological and respiratory endpoint listed above will be plotted versus visit and by arm within each plot.

For capillary blood lactate levels during the VO₂max test, we will fit a 4 parameter sigmoidal model for each arm at V3 and V43 respectively. Letting y_{ij} be the lactate of subject i at time *j*, we have

$$y_{ij} = (\beta + \beta_i) + \frac{\alpha - (\beta + \beta_i)}{1 + \exp\left\{\delta(\ln\left(W_{ij}\right) - \ln\left(\eta + \eta_i\right))\right\}} + \varepsilon_{ij}$$

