where W_{ij} is the work rate for subject *i* at time *j* α and β are the minimum and maximum lactate levels respectively. The parameter η_i represents the workrate that elicits a response midway between α and β_i , and δ is a shape parameter. Lastly, the error term is modelled as ε_{ij} . Note that β_i and η_i are modelled as random effects to allow for variations in the lactate curve between subjects. An example of the sas code is as shown below, starting parameters may be found using proc nlin without the random effects. The number of random effects may be adjusted depending on model fit.

```
proc nlmixed data= data ;
  parms b0=xx e0=xx a=xx d=xx s2=xx s2b1=xx s2b2=xx cb12=xx;
  beta = b0 + bi;
  eta = e0 + ei;
  pred = beta+(a-(beta))/(1+exp(d(ln(w)-ln(eta))));
  model vo2 ~ normal(pred,s2);
   random bi ei ~ normal([0,0],[s2b1,cb12,s2b2]) subject=subject;
run;
```

Using the fitted models, we will back-calculate the value of W^* (conditional on β_i and η_i) that elicits a response of y=4 mmol (Heck 1985) using the following formula for each arm and visit.

$$W^* = \hat{\eta} \left(\frac{\hat{\alpha} - 4}{4 - \hat{\beta}} \right)^{\frac{1}{\hat{\delta}}}$$

Note that $\hat{\alpha}$, $\hat{\beta}$, $\hat{\delta}$ and $\hat{\eta}$ are the respective estimates from the fitted model. Within each arm, we will present the change in workload at a lactate level of 4mmol from V3 to V43. The mean curve estimated from the model for Cigarette, IQOS-1, IQOS-2 and SA will be plotted versus workload for each arm and visit, in these plots a horizontal line at 4 mmol will be drawn as well. The same plot will be done for Cigarette, IQOS-1, IQOS-2, Dual-1 and Dual-2.

For the endpoints VO₂ and heart rate (V4 and V43), a linear mixed effects model will be used with the restricted maximum likelihood method for estimation of the parameter in the various (cigarette, IQOS-1 and SA) arms versus workload. Each endpoint will be fitted with workload, age, visit, sex, arm, visit*arm, baseline cigarette consumption at V1 and daily cigarette

Data and information contained in this document are considered to constitute trade secrets and confidential commercial information, and the legal protections provided to such trade secrets and confidential information are hereby claimed under the provisions of applicable law. No part of this document may be publicly disclosed without the written consent of Philip Morris Products S.A

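### Lactate-threshold analysis (SAP 9.6.1.1.4): the example code names the wrong response, a resting sample coded 0 W cannot enter the log curve, and the V3-to-V43 change has no stated interval or link between visits

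*SAP*

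**What the plan says.** - **Model text (SAP 9.6.1.1.4).** For capillary lactate, "we will fit a 4 parameter sigmoidal model for each arm at V3 and V43 respectively". The response is defined before the equation: "Letting y_{ij} be the lactate of subject i at time *j*, we have". Work rate enters through its logarithm. Alpha and beta are the lowest and highest lactate levels, and beta and eta carry subject random effects.
- **Code.** It is introduced with "An example of the sas code is as shown below". The predictor begins "pred = beta+(a-(beta))/(1+exp(d(ln(w)-ln(eta" and the response line begins "model vo2 ~ normal(pred,s2". There is no visit term and no covariance between visits.
- **Result.** The 4-mmol workload is described as conditional on the subject effects, yet is computed per arm and visit. Within each arm, "we will present the change in workload at a lactate level of 4mmol from V3 to V43". No standard error, interval or pairing rule is given. The outputs are Table 15.2.2.4.3.1 and Figures 15.1.4.1 and 15.1.4.2.
- **Sampling.** Protocol 7.6.1 has lactate taken while the subject sits on the ergometer before pedalling, and again at each 25 W step. SAP 9.6.1.2.4 includes the resting value in the summaries. No rule says how it enters the curve.
- **Post-exercise sample.** Protocol 7.6.1: "The final blood sample should be obtained within 5 minutes after termination of the bike exercise". Protocol Appendix 1, footnote 17: "The final blood sample should be obtained 60 sec after termination of the bike exercise". SAP Table 13-1, footnote 16, repeats the 60-second version.

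**The concern.** Lactate belongs to Objective 4. Protocol 4.3 values it, together with blood volume, because it does not depend on how hard the subject is willing to try. As the section stands, the programmer has to settle four things without a prespecified rule: which variable is the response, what happens to the resting sample, whether the 4-mmol workload belongs to the subject or to the arm, and how precise the change is.

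The last matters most. The study tests no hypotheses (SAP 3.3.1), so estimates and intervals are its product. Protocol 12.5 foresees 95% intervals for between-arm differences in this objective. The same SAP subsection gives intervals for the blood-composition and respiratory parameters, but none for lactate.

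**Working it through.** The plan states no figure for this analysis, so there is none to reproduce. The curve values, standard deviations and correlations below are assumptions; the documents give none.

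**1. Inverse formula, with lactate as response.** The stated curve is y = beta + (alpha − beta)/(1 + (W/eta)^delta), because exp{delta(ln W − ln eta)} = (W/eta)^delta. Setting y = 4 gives (W/eta)^delta = (alpha − 4)/(4 − beta), which is the SAP's formula. With alpha 1, beta 12, delta 3 and eta 180, the ratio is (−3)/(−8) = 0.375 and the workload is 180 × 0.375^(1/3) = 129.8 W. Put back into the curve, this returns 4.0. The formula is right.

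**2. The same formula with VO2 as response.**
- Asymptotes of 300 and 2800 mL/min: (300 − 4)/(4 − 2800) = −0.106.
- Asymptotes of 0.3 and 2.8 L/min: (0.3 − 4)/(4 − 2.8) = −3.08.

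Both ratios are negative, so the workload is undefined. The code as printed cannot produce the planned table.

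**3. Resting sample.** That rest means 0 W is an inference from the seated rest before loading; the documents do not write it. If it is coded 0, ln(0) is undefined and the record is lost, although the curve itself has the finite limit alpha there. With a 200 W peak there are 200/25 = 8 steps plus rest, so rest is 1 of 9 values (11%). The share is 20% for a 100 W peak and 8% for 300 W, not counting the post-exercise sample.

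An illustrative simulation used 400 runs, 20 subjects, the curve in step 1 and a pooled fit without random effects:

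| | Rest kept at its limit | Rest dropped |
|---|---|---|
| Mean 4-mmol workload | 127.1 W | 127.1 W |
| SD of estimated alpha | 0.053 | 0.081 |

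Dropping rest did not move the reported quantity. It made the lower asymptote less precise.

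**4. Precision of the change.** Take n subjects, SD s at each visit and correlation rho between visits. The SE of the mean change is s·sqrt(2(1 − rho)/n) if paired and s·sqrt(2/n) if the visits are treated as independent. The ratio is 1/sqrt(1 − rho).

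| Assumed rho | SE, independent / paired |
|---|---|
| 0.3 | 1.20 |
| 0.5 | 1.41 |
| 0.7 | 1.83 |
| 0.8 | 2.24 |

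In watts, with n = 20, between-subject SD 25 and within-subject SD 15: s = sqrt(625 + 225) = 29.2 and rho = 625/850 = 0.74. The SE is 9.2 W treated as independent and 4.7 W paired.

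**5. Post-exercise sample.** A sample at 4 minutes satisfies Protocol 7.6.1 but not the two footnotes. No workload is being produced when it is drawn, and no section says whether it enters the curve or at what wattage.

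**The case against.** The strongest reply is that the planned analysis is plainly of lactate. The definition of the response, the equation, the 4-mmol back-calculation, the figure titles and the table title all agree; only one line of code offered as an example does not. Because a VO2 response leaves the result undefined, the slip would show at once and could not quietly bias anything. That stands: a reader might infer that the SAP analyses the wrong variable, and the documents do not support it.

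On rest, no section says that the value enters the fit or is coded 0, and the low-wattage steps also inform the lower asymptote. A reader might infer that the 4-mmol workload would be biased; the simulation shows no such effect.

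On pairing, the SAP never says that the visits will be treated as independent. Its wording about conditioning on the subject effects leaves room for subject-level workloads that could be paired, and it promises a change within each arm. An over-wide interval would also err on the cautious side. So the SE factors describe what one unstated choice would cost, not what the SAP prescribes. The gap remains, because neither the level of the quantity nor its interval is specified.

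On sampling time, Protocol Appendix 5 records a change from 60 seconds to 5 minutes in 7.6.1, so the footnotes may simply not have been carried along. A sample at 60 seconds meets both statements. The texts still differ.

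With at most 25 randomised per training arm, a joint nonlinear model may not converge. That is fair, and the fix therefore needs a fallback.

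**Conclusion.** The point holds as a set of specification faults in one Objective 4 analysis.

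- **Certain from the text:** the example code contradicts the model; the change has no stated interval and no link between visits; the post-exercise sampling time is stated in two ways.
- **Inferred:** rest values would be lost if coded 0 W, probably with little effect on the 4-mmol workload.
- **Conditional:** an SE too large by 1.4, 1.8 or 2.2 times rests on assumed correlations of 0.5, 0.7 or 0.8 and on an independence calculation that the SAP does not state. The error would hide a change, not create one.

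A reader might also take lactate to be the only measure that the protocol regards as free of motivation. Protocol 4.3 says the same of blood volume.

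Nothing here touches the VO2max or exercise-capacity analyses. The consequences are confined to the lactate table and plots.

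**What to change.** 1. Name lactate as the response in the code.
2. Write the curve as beta + (alpha − beta)/(1 + (W/eta)^delta). It is algebraically the same curve and equals alpha at W = 0 for delta > 0, so the resting sample is kept.
3. Fit V3 and V43 jointly within each arm, with a visit effect on eta and correlated subject effects. If that does not converge, compute the 4-mmol workload for each subject at each visit and analyse the paired differences. State in advance what triggers the fallback.
4. Report the change with its 95% CI.
5. State that the post-exercise sample is not assigned a workload in the curve, and reconcile Protocol 7.6.1 with Protocol Appendix 1 footnote 17 and SAP Table 13-1 footnote 16.

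The cost is SAP code and wording plus aligning two footnotes; no new data are needed. The downside is that the joint nonlinear model may need simpler random effects, which is why the paired analysis should be written in as the fallback.

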An appropriate statistical model will be used to estimate the changes in physiological parameters and perception of exertion and capacity whilst adjusting for covariates such as age, sex, cigarette consumption or any other clinically relevant covariates of interest. The difference between arms will be estimated and reported together with its 95% confidence intervals. Other covariates may be added as needed.

Data and information contained in this document are considered to constitute trade secrets and confidential commercial information, and the legal protections provided to such trade secrets and confidential information are hereby claimed under the provisions of applicable law. No part of this document may be publicly disclosed without the written consent of Philip Morris Products S.A

Philip Morris Products SA	Clinical Study Protocol	Confidential
P1-EXC-01-EU	Version 3.0 / 2 May 2019	Page 16 of 151

Descriptive statistics of the various measures of physical activity as measured by the mHealth wearable device will be reported. An appropriate statistical (linear or non-linear) model will be used to estimate the levels of activity taking into account clinically relevant covariates and repeated measures over time. Comparisons of physical activity levels for *IQOS*-1 and *IQOS*-2 arm will be reported based on the chosen statistical model.

For each of the biological markers descriptive statistics will be employed to assess the difference between arms. An appropriate statistical model may be employed to estimate differences across arms at V43.

For weight, body fat and waist circumference, descriptive statistics will be employed to assess the changes for each arm. An appropriate statistical model may be employed to estimate differences across arms at V43.

To monitor levels of exposure to CO descriptive statistics of exhaled CO will be summarized and presented for each arm. Descriptive statistics of COHb% in blood, NEQ, NNAL and CEMA in urine will be summarized and presented for each arm. An appropriate statistical model may be employed to estimate differences across arms during the visits where these are measured.

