# Endpoints (V3, V43)

- Blood composition: Hemoglobin mass (g), red blood cell volume (mL), plasma volume (mL) and total blood volume (ml) as determined by CO re-breathing method
- Capillary blood lactate levels during VO2max test (mmol/L)
- Perceived rate of exertion during VO2max test (Borg Rating of Perceived Exertion (RPE) scale)

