# Endpoints (V3, V4 and V43)

- Respiratory parameters at VO2max: Ventilation (L/min), respiratory rate, VCO2 (L/min), Respiratory exchange ratio (RER) (VCO2 / VO2)
- Rating of Perceived Capacity (RPC) scale
- Heart rate (bpm) and oxygen uptake (mL/min) during VO2max test
  - 5. To monitor trends of daily physical activity levels during the study in subjects switching to *IQOS* (with and without training), continuing to smoke cigarettes (with training) and being smoking abstinent (with training)

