### **Confidentiality Statement**

Philip Morris Products SA	Clinical Study Protocol	Confidential
P1-EXC-01-EU	Version 3.0 / 2 May 2019	Page 105 of 151

cigarette consumption and/or *IQOS* may also be used as a covariate. Further details will be provided in the SAP.

Estimates of variability from the statistical model will be reported and may be used to power future similar studies.

Descriptive statistics will be used to present various measures assessing the intensity of exercise training in each arm. This includes the cumulative work produced (calories and calories/kg body weight), average work rate during each training session (watt and watt/kg body weight), average work rate during each interval during each training session (watt and watt/kg body weight), time spent at 0-50%, 50-65%, 65-75%, 75-90%, >90% of maximal work rate during each training session (min:sec), average heart rate (HR) during each training session (bpm) and time spent at 0-50%, 50-60%, 60-70%, 70-80 % and >80 % of maximal HR during each training session (min:sec).

To evaluate changes in physiological parameters and perception of exertion and capacity in subjects switching to *IQOS*, continuing to smoke cigarettes and being smoking abstinent

An appropriate statistical model will be used to estimate the differences in physiological parameters and perception of exertion and capacity whilst adjusting for covariates such as age, sex, cigarette consumption and/or *IQOS* use or any other clinically relevant covariates of interest. The difference between arms (*IQOS*-1/SA vs cigarette) will be estimated and reported together with its 95% confidence intervals. All other pairwise comparisons between arms will be estimated and reported as well.

To monitor trends of daily physical activity levels during the study in subjects switching to *IQOS*, continuing to smoke cigarettes and being smoking abstinent

Descriptive statistics of the various measures of physical activity as measured by the mHealth wearable device will be reported. An appropriate statistical (linear or non-linear) model will be used to estimate the levels of activity taking into account clinically relevant covariates such as sex, cigarette consumption and age, and repeated measures over time. Estimates for each arm and all pairwise comparisons between arms will be reported using an appropriate statistical model as defined in the SAP.

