9.6.1.2.4 Physiological parameters and perception of exertion and capacity

For blood composition recorded values and derived (or computed) values as well as the changes from baseline will be listed and commonly summarized by arm. Derived endpoints (Hbmass, RBCV, BV, and PV) are described in Section 5.2 "Blood composition as determined by CO re-breathing method". Lactate values (continuous) and Borg RPE scale values (categorical) will be listed; they will be summarized within each study arm (and overall) for each visit at rest and at each 25 Watt workload increase.

For the BORG scale, a mosaic plot showing the number of subjects with BORG scale > 16 and the number of subjects with BORG scale < 16 (y-axis) versus maximum wattage during the VO2max test (x-axis) will be plotted separately for each study arm.

Respiratory parameters (continuous) with changes from baseline and Rating of Perceived Capacity (RPC) scale values (categorical) will be listed and summarized. Both acute and

Data and information contained in this document are considered to constitute trade secrets and confidential commercial information, and the legal protections provided to such trade secrets and confidential information are hereby claimed under the provisions of applicable law. No part of this document may be publicly disclosed without the written consent of Philip Morris Products S.A

Philip Morris Products SA.	Statistical Analysis Plan	Confidential
P1-EXC-01-EU	Final 2.0	Page 50 of 71
Related to PMI-RRP-WKI-112487		CAD DI EVC AL EU

training baseline will be presented for these parameters as well. Although the RPC is a categorical (actually ordinal) scale it will be summarized as a continuous variable by visit, arm and stratified by sex. Scatter plots of the RPC scale vs the corresponding VO₂max value at each visit will be plotted.

Heart rate and oxygen uptake (VO_2) will be listed; these data will be summarized within each study arm for each visit at rest and at each 25 Watt workload increase.

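### Lactate workload, Borg RPE and RPC are given no between-arm estimate in the SAP, although the protocol commits to between-arm differences with 95% CIs for objective 4, and the SAP does not declare the departure

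*SAP*

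**What the plan says.** **Protocol.** For objective 4, section 12.5 commits to a model whose purpose is to "estimate the differences in physiological parameters and perception of exertion and capacity whilst adjusting for covariates such as age"; the covariates it goes on to name are sex and the subject's use of cigarettes or IQOS. It continues: "The difference between arms (*IQOS*-1/SA vs cigarette) will be estimated and reported together with its 95% confidence intervals". It then adds: "All other pairwise comparisons between arms will be estimated and reported as well". The synopsis makes the same commitment in shorter form: "The difference between arms will be estimated and reported together with its 95% confidence intervals". Section 3.1 lists capillary lactate and Borg RPE (V3, V43) and RPC (V3, V4, V43) under this objective.

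**SAP.** Section 9.6.1.1.4 gives within-arm and between-arm estimates with 95% CIs, following Tables 4 and 5, for four blood composition and four respiratory parameters. For lactate it fits a four-parameter sigmoid to each arm at each of V3 and V43 and back-calculates W*. It then says "Within each arm, we will present the change in workload at a lactate level of 4mmol from V3 to V43", with mean curves plotted by arm. For the lactate values and Borg ratings, section 9.6.1.2.4 says "they will be summarized within each study arm (and overall) for each visit at rest and at each 25 Watt workload increase". RPE also has a mosaic plot for each arm. RPC is summarised as a continuous variable by visit, arm and sex, and plotted against VO2max.

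Section 7 of the SAP, on changes from the protocol, lists only the exploratory analysis with biochemical verification.

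**The concern.** The protocol commits to an estimated comparison, and the SAP replaces it for three endpoints with per-arm displays without saying so.

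The form of the lactate output matters in this design. IQOS-1, SA and cigarette subjects all follow the same 38-session programme and repeat the same test. An improvement from V3 to V43 is expected in each of them whatever they smoke or use. The question in Protocol 4.2 is comparative: whether lower CO exposure changes the response to training relative to continued smoking. A before-after change in one arm does not answer it.

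These endpoints also support the main result. Protocol 4.3 includes lactate among the measures that do not depend on how hard the subject is willing to try. That is useful in an open-label study whose site staff know the allocation.

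**Working it through.** No sample size, power or alpha figure is involved. The check compares the two documents endpoint by endpoint.

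**1. Commitment against delivery for objective 4.** Protocol 3.1 lists six entries.

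| Entry | SAP analysis | Between-arm difference with 95% CI specified? |
|---|---|---|
| Blood composition | Mixed model, change from baseline | Yes (Table 5) |
| Respiratory parameters | Mixed model, change from baseline | Yes (Tables 4 and 5) |
| Lactate | Separate sigmoid per arm and visit; change in W* within each arm | No |
| Borg RPE | Summaries, mosaic plot | No |
| RPC | Summaries, scatter plot | No |
| Heart rate and VO2 by workload | Mixed model with arm and visit-by-arm terms; curves and coefficients reported | None stated, but the model contains the terms |

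The point rests on the third to fifth rows. The lactate model also carries none of the covariates named in Protocol 12.5, and no CI is stated for the change in W*. RPC otherwise appears only as a candidate covariate in the VO2max and exercise capacity models.

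**2. Table list (SAP 13.2).** Lactate has one analysis table, 15.2.2.4.3.1. RPC has a descriptive table, 15.2.2.4.7.1. There is no between-arm table for RPE or RPC.

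**3. Was a descriptive treatment intended?** Protocol 12.5 says a model *may* be employed for health markers, body measurements and exposure. For objective 4 it says a model *will* be used. SAP 9.6.1.1.6 supplies Table 5 contrasts for the health markers, which were optional.

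**4. What a within-arm change estimates.** Write the mean V3-to-V43 change in trained arm a as g + p(a). Here g is the training and retest effect common to the trained arms, and p(a) is the part that depends on product, including any effect of product on trainability.
- Within IQOS-1: g + p(IQOS-1). The two parts cannot be separated.
- IQOS-1 minus cigarette: [g + p(IQOS-1)] − [g + p(cig)] = p(IQOS-1) − p(cig).

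Only the second removes g.

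**5. The W* formula.** Setting y = 4 in the SAP's curve gives (α − β)/(4 − β) = 1 + (W/η)^δ. Hence (W/η)^δ = (α − 4)/(4 − β) and W* = η[(α − 4)/(4 − β)]^(1/δ), as the SAP has it. The formula is right; the contrast is missing.

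**6. Why a two-stage repair would not do.** A tempting repair is to predict W* for each subject from the random effects and analyse those predictions by arm. Because each arm and visit is fitted separately, predictions are pulled toward their own arm's mean. In a linear analogue with reliability λ, a prediction is mean + λ(x − mean). The apparent SD is λ times the true SD, while the sampling error of the arm mean is unchanged, so the CI is λ times its correct width. With 20 per arm (38 df, critical value 2.024) and no true difference, the nominal 5% error becomes P(|t| > 2.024λ):
- λ = 0.9: P(|t| > 1.822) = 8%
- λ = 0.7: P(|t| > 1.417) = 16%
- λ = 0.5: P(|t| > 1.012) = 32%

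The λ values are assumptions, since the documents give none. They affect the choice of remedy, not the size of the finding.

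**The case against.** **The study is descriptive and tests no hypothesis** (Protocol synopsis and 12.1.5; SAP 3.3.1). True, but the commitment is to estimates with intervals, not tests, and the SAP honours it for sibling endpoints.

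**The lactate table may hold a contrast.** Table 15.2.2.4.3.1 is titled as an analysis, like the tables that carry between-arm estimates, and its shell is in a separate document. This stands as a limit: it cannot be said that no lactate contrast will ever be produced. But the SAP text defines none, and the argument does not reach RPE or RPC.

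**The arms are shown side by side.** This also stands. A reader might infer that the cigarette arm never enters any comparison. The SAP does not support that: the change in W* is given for every arm, and the cigarette curve is plotted with the others. A shared improvement would be visible, and an unadjusted difference could be had by subtraction. What is missing is the adjusted difference and its interval.

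**Changes may be documented in the study report** (Protocol 12.1; SAP 1). This permits later disclosure. It does not supply a prespecified contrast.

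**Lactate is not the only such measure.** A reader might infer from Protocol 4.3 that it is. That section says the same of blood volume, which does get Table 5 contrasts. One effort-independent measure is therefore already compared between arms, which lowers the stakes.

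**Conclusion.** The discrepancy is real and undeclared. For lactate W*, Borg RPE and RPC, the SAP text defines no controlled between-arm estimate with an interval, although Protocol 12.5 commits to one. It concerns three of six entries under one non-primary objective of an exploratory study, and it should be corrected without being treated as critical.

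No numerical magnitude is attached. A reader might go on to calculate how often a within-arm interval would exclude zero under a shared training gain and read that as a false-positive rate. The documents do not support this: the SAP plans no interval or test for the within-arm change in W*, and the documents give neither an SD for W* nor an expected gain.

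The reading assumes that the trained arms follow the common programme as written. SAP arms are actual-use groups in the exercise-compliant set, so a Table 5 contrast would compare concurrently trained groups and would not be a strict randomised comparison. It would still remove the shared training and retest effect.

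**What to change.** In SAP 9.6.1.1.4:

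1. **Lactate.** Fit one joint nonlinear mixed model over all arms and both visits, with arm-by-visit parameters. Report the Table 5 between-arm differences in change of W* with 95% CIs, by the delta method or a subject-level bootstrap, in Table 15.2.2.4.3.1. Do not carry subject-level W* from separate arm-and-visit fits into a second model. Include the Protocol 12.5 covariates where the model supports them, or declare their omission. The example code names VO2 as the response and should be corrected to lactate.
2. **RPC.** The SAP already summarises it as continuous. Fit the change-from-baseline mixed model used for respiratory parameters at V4 and V43, with Table 4 and Table 5 contrasts.
3. **Borg RPE.** Give a Table 5 contrast at a prespecified workload common to V3 and V43. Choose an ordinal or linear model before unblinding.
4. **Labelling.** Mark within-arm changes as uncontrolled. Declare in section 7 any endpoint left descriptive only.

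The cost is SAP wording, one refitted model and a few added outputs on data already collected. Study conduct does not change.
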